## **Inclusion criterias**

**Participants must meet the following three conditions:**

- A. Women over 21 years old (inclusive) and under 65 years old (inclusive), who have never received total hysterectomy and never received radiation therapy for the uterus / cervix
- B. Understand the content of the experiment and sign the subject's consent form
- C. meet one of the following 5 conditions :

1. No history of abnormal smear or cervical lesions
2. There have been mild smears or pathological abnormalities within 3-12 months, and those who need to receive Pap smear follow-up

Mild smear abnormalities include atypical squamous cell of undetermined significance, first-degree cervical intraepithelial neoplasia grade 1, or atypical glandular cell.

3. Those who have had moderate to severe smear or pathological abnormalities or cervical cancer, have undergone conical surgery, and are currently receiving follow-up

Including atypical squamous cells favor high-grade squamous intraepithelial lesion in smear, cytopathic lesion cannot exclude high-grade squamous intraepithelial lesion, smear or histopathology is cervical intraepithelial neoplasia of the second degree lasia grade 2, cervical intraepithelial neoplasia grade 3, cervical carcinoma in situ, squamous cell carcinoma of the cervix, or atypical glandular cells favor neoplasm, adenocarcinoma in situ of the cervix, or Cervical adenocarcinoma patients.

4. Mild smear or pathological tissue abnormalities within 3 months without treatment

Mild smear abnormalities include atypical squamous cell of undetermined significance, first-degree cervical intraepithelial neoplasia grade 1, or atypical glandular cell.

5. Moderate or severe abnormalities in smear or pathological tissue or cervical cancer found within 3 months, and those who have not received treatment

Including atypical squamous cells favor high-grade squamous intraepithelial lesion in smear, cytopathic lesion cannot exclude high-grade squamous intraepithelial lesion, smear or histopathology is cervical intraepithelial neoplasia of the second degree lasia grade 2, cervical intraepithelial neoplasia grade 3, cervical carcinoma in situ, squamous cell carcinoma of the cervix, or atypical glandular cells favor neoplasm, adenocarcinoma in situ of the cervix, or Cervical adenocarcinoma patients.

stratification of the statistical analysis of this experiment.

## **Exclusions criterias**

### **Subjects who meet any of the following conditions cannot participate in this trial:**

- A. Those who have undergone total hysterectomy (those who have undergone subtotal hysterectomy and still retain the cervix do not need to be excluded)
- B. pregnant
- C. with cervicitis who must be treated
- D. Those who have received treatment for cervical lesions within 90 days
- E. who have received or are receiving uterine / cervix or vaginal radiation therapy
- F. Women under the age of 21 or over the age of 65
- G. 48 hours before having sex without a condom
- H. Excessive vaginal secretions, such as excessive transparent mucus during ovulation
- I. Those who are receiving local treatment for vaginitis and have drugs in the vagina
- J. Menstrual period, the menstruation has not ended

## **Outcome measures**

### **Primary evaluation indicators:**

- A. HPV16, 18, 31, 33, 35, 39, 45, 51, 52, 56, 58, 59, 66, 68 and other 14 types are high-risk cancer-causing types. Therefore, the main purpose of the agreement is whether there is high-risk HPV detected in the samples collected by doctors and self - sampled . Consistency is defined as follows:
- B. The high-risk HPV test results are consistent (agree) , and the test results show that both of them have any of the above-mentioned high-risk HPV or neither of them has high-risk HPV .
- C. The test results of high-risk HPV are inconsistent ( disagree ). One of the samples collected by doctors and self- collected samples does not have any of the above-mentioned high-risk HPV types , and the other has any of the above-mentioned high-risk types.
- D. The consistency between the test results of the samples collected by the physician and the test results of the subjects' self- collected samples will be evaluated by Cohen 's kappa coefficient or compared with related tests.

### **Secondary evaluation indicators:**

- A. The success rate (proportion of effective specimens) of HPV typing in physician - collected and self- collected specimens of all detectable HPV types.
- B. The incidence of adverse reactions was used as the safety evaluation index to evaluate whether there would be adverse reactions caused by doctors' self-examination of vaginal secretions or self-examination of vaginal secretions. The test process was recorded according to the grading standard of CTCAE version 5.0 .
- C. Evaluate whether women can complete effective self-specimen sampling by following the instructions or videos. The beta-globin of the test results will be used as an evaluation index for valid specimens, and the reliability of the explanatory files will be evaluated by the results of the questionnaire survey.
- D. -collection success rate (proportion of effective specimens) and consistency evaluation of each group under the test group .
- E. The correlation between the HPV test results collected by physicians , the HPV test results of self- collected samples, and the results of Pap smear and histopathological diagnosis at the same time . Taking the most serious pathological diagnosis as the standard, calculate
  1. Predict the sensitivity, specificity, positive predictive value and negative predictive value of cervical lesions based on the HPV test results of the samples taken by doctors
  2. Predict the sensitivity, specificity, positive predictive value and negative predictive value of cervical lesions based on the test results of self- collected samples
- F. The questionnaire was used to evaluate the satisfaction of the subjects' self-testing .

## Statistical considerations

### Statistical design, methods and analysis procedures

A. This study is a multi-center clinical trial in Taiwan to test the blindness of operators . It mainly explores the consistency between self- testing of products and doctor -testing . In this experiment, the test results of samples collected by doctors will be used as the standard, and compared with the results of HPV type test of samples collected by the same subject to verify the consistency of HPV types in samples collected by doctors and self- sampled samples.

B. The experimental design uses the status of cervical precancerous lesions as a stratification variable, and the 5 groups of test groups are divided into the following proportions:

5 groups of subjects included in the subjects	Inclusion ratio
1. No history of abnormal smear or cervical lesions	10%
2. There have been mild smears or pathological abnormalities within 3-12 months, and those who need to receive Pap smear follow-up	15%
3. Those who have had moderate to severe smear or pathological abnormalities or cervical cancer, have received conical surgery , and are currently receiving follow-up	20 %
4. Mild smears or pathological tissue abnormalities within 3 months, who have not yet been treated	20 %
5. Moderate and severe abnormalities in smear or pathological tissue or cervical cancer found within 3 months, and those who have not received treatment	35%

According to relevant literature research, it is estimated that the positive probability of HPV in the five groups is (1) 10% , (2) 70% , (3) 50%, ( 4 ) 70% , ( 5 ) 90%, depending on the experimental design Under the stratum recruitment ratio , the overall HPV positive rate is expected to be about 67% , as shown in the table below .

Stratification	AI location rate	S stratified HPV positive prob.
1. No history of abnormal smear or cervical lesions	0.1	0.1
2. There have been mild smears or pathological abnormalities within 3-12 months, and those who need to receive Pap smear follow-up	0.15	0.7

3. Those who have had moderate to severe smear or pathological abnormalities or cervical cancer, have received conical surgery , and are currently receiving follow-up	0.20	0.5
4. Mild smears or pathological tissue abnormalities within 3 months, who have not yet been treated	0.20	0.7
5. Moderate and severe abnormalities in smear or pathological tissue or cervical cancer found within 3 months, and those who have not received treatment	0.35	0.9
Total	0.67	

C. Subjects who meet the admission requirements will be included in one of the 5 stratified groups according to their pathological conditions. All test institutions will accept cases through competition. After the stratified groups reach the predetermined acceptance ratio, no subjects from this group will be recruited.

D. In this experiment, each subject will provide two specimens, one from a doctor's examination and one from a self- examination . In order to maintain the scientific nature of the consistency assessment, the tester will be blinded , that is, the tester cannot know the samples corresponding to the two collection methods of any subject.

E. This study intends to achieve the blindness requirement by means of coding, that is, the sample number collected by the doctor is the number of the subject of this study (the number is given according to the order of admission ), and the self- collected sample of the same subject is based on the sample number collected by the doctor, and the number obtained by random garbled operation makes it impossible to directly correspond to the sample collected by the doctor .

F. According to the main evaluation indicators of the test, the consistency of this study is defined as : for 14 high-risk types such as HPV16, 18, 31, 33, 35, 39, 45, 51, 52, 56, 58, 59, 66, 68, the main purpose is to list the consistency (agreement) of the detection in the doctor's inspection and self- sampling samples . Consistency is defined as follows:

- (1) The high-risk HPV test results are consistent (agree) , and the test results show that both of them have any of the above-mentioned high-risk HPV or neither of them has high-risk HPV ..
- (2) The test results of high-risk HPV are inconsistent ( disagree ). One of the samples collected by doctors and self- collected samples does not have any of the above-mentioned high-risk HPV types , and the other has any of the above-mentioned high-risk types .

According to the definition of the test result, a contingency table can be obtained as follows, the Kappa statistic  $K = (P_0 - P_c) / (1 - P_c)$  for statistical verification, where  $P_0 = (a+d) / (a+b+c+d)$  is the observed agreement (observed agreement), and  $P_c = \left( \frac{cm_1 \times rm_1}{n} \right) + \left( \frac{cm_2 \times rm_2}{n} \right) / n$  is the theoretical expected

agreement (chance agreement). The standard error of the Kappa statistic is based on Fleiss, Cohen, and Everitt (1969) as  $SE(K) = SD(K)/\sqrt{N}$ , where  $SD(K) = \sqrt{P_0(1 - P_0)/(1 - P_c)^2}$ . The 100(1- $\alpha$ )% interval estimate of the Kappa statistic is  $K \pm z_{\alpha/2} SE(K)$ .

		Physician check		sum
		High-risk HPV detected	No high-risk HPV detected	
self - test	High-risk HPV detected	a	b	rm1
	No high-risk HPV detected	c	d	rm2
	sum	cm1	cm2	no

For each HPV type ( type-specific) , the consistency between the test results of the samples collected by the physician and the samples collected by the subjects will be evaluated by Cohen 's kappa coefficient or compared with related tests.

- G. Consistency assessment will take valid samples as the analysis group, that is, the same subject's verification physician and self- sampling samples are all valid samples.
- H. A valid sample is defined as a positive test for the  $\beta$ -globin gene in the internal control group of Jingyu Human Papillomavirus Genotyping Detection Kit . The intent-to-treat group (ITT) was used as the analysis group for safety, self- collection success rate, and satisfaction evaluation.

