# **Subject inclusion conditions**

Subjects must meet the following three conditions:

- A. aged 21 years and above (inclusive) and below 65 years old (inclusive) who have not undergone total hysterectomy and uterine / cervical radiation therapy
- B. Understand the trial content and sign the subject consent form
- C. Those who meet one of the following 5 conditions:
- 1. Those with no abnormal smears or history of cervical lesions
- 2. Those who have had mild smear or pathological tissue abnormalities within 3-12 months and need to undergo cervical smear follow-up

Mild smear abnormalities include atypical squamous cells of undetermined significance, cervical intraepithelial neoplasia grade 1, or atypical glandular cells.

3. Have had moderate to severe smear or pathological tissue abnormalities or cervical cancer, have undergone cone surgery, and are currently being followed

Including smear is atypical squamous cells favor high-grade squamous intraepithelial lesion atypical squamous cells favor high-grade squamous intraepithelial lesion, the cytopathology cannot exclude high-grade squamous intraepithelial lesion dysplasia cannot exclude high-grade squamous intraepithelial lesion, smear or histopathology is Cervical intraepithelial neoplasia grade 2, Cervical intraepithelial neoplasia grade 3, Cervical carcinoma in situ, Cervical squamous cell carcinoma, or atypical glandular cells favor neoplasm, cervical adenocarcinoma in situ, or cervical adenocarcinoma.

4. Those who have mild smear or pathological tissue abnormalities within 3 months and have not yet been treated

Mild smear abnormalities include atypical squamous cells of undetermined significance, cervical intraepithelial neoplasia grade 1, or atypical glandular cells.

5. Those who have found moderate to severe smear or pathological tissue abnormalities or cervical cancer within 3 months and have not yet received treatment

Including smear shows atypical squamous cells favor high- grade squamous intraepithelial lesion, smear test or histopathology is Cervical intraepithelial neoplasia grade 2, Cervical intraepithelial neoplasia grade 3, Cervical carcinoma in situ, Cervical squamous cell carcinoma, or atypical glandular cells favor neoplasm, cervical adenocarcinoma in situ, or cervical adenocarcinoma.

The above groupings are also the basis for stratification of the statistical analysis of this trial.

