## Test Hypothesis and Verification

Null hypothesis (H0 ): The high-risk HPV test results of the samples collected by physicians and those collected by subjects themselves were consistent with Cohen 's kappa coefficient  $k \leq 0.66$ .

Alternative Hypothesis (H1 ): The high-risk HPV test results of the samples collected by the physician and the samples collected by the subjects themselves are consistent with Cohen 's kappa coefficient  $k > 0.66$ .

If the test results show that the opposite hypothesis is established, the expected goal of the test is achieved.

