## Sample size calculation

The above-mentioned kappa value is preset to be 0.72, under the condition that the test power is 80% and the significance level is 0.05, according to the proportion of subjects included in each group, the required samples are 1,049 cases . Considering that there are up to 10% of invalid samples and patients requesting to withdraw from the trial, the trial is expected to recruit 1,200 subjects , and the number of subjects assigned to each group is as follows according to the original test group ratio.

5 groups of subjects included in the subjects	Inclusion ratio	Estimated number of people included
1. No history of abnormal smear or cervical lesions	10%	120 people
2. There have been mild smears or pathological abnormalities within 3-12 months, and those who need to receive Pap smear follow-up	15%	180 people
3. Those who have had moderate to severe smear or pathological abnormalities or cervical cancer, have received conical surgery, and are currently receiving follow-up	20 %	240 people
4. Mild smears or pathological tissue abnormalities within 3 months, who have not yet been treated	20 %	240 people
5. Moderate and severe abnormalities in smear or pathological tissue or cervical cancer found within 3 months, and those who have not received treatment	35%	420 people
The total number of subjects expected to be included		1,200 people

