### **In multi-center clinical trials, the minimum and maximum number of subjects included in each trial institution**

- A. This trial adopts a competitive type of case acceptance, and the case will stop after the expected number of trial subjects is included.
- B. each test institution will allocate 10 test work bags that meet the conditions of the subjects . According to the acceptance speed of each test institution, when the test work bags are estimated to be used up, an application should be submitted to the test commissioner to supplement the next batch of test work bags to make the test run smoothly.
- C. Based on the above, in this trial, each trial institution will include a minimum of 50 subjects, but there is no standard for the maximum number of subjects.

Except for the analysis of the main evaluation indicators and secondary evaluation indicators in this trial, the rest of the data analysis is exploratory analysis.

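### Does the pooled primary kappa need a combined group-stratified kappa beside it, given five quota groups with planned HPV rates from 10% to 90%?

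*SAP*

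**What the plan says.** The protocol, under Subject inclusion conditions, lists five groups by lesion status and adds: "The above groupings are also the basis for stratification of the statistical analysis of this trial". The SAP (Statistical design, methods and analysis procedures, item B) says the same of the design: "The experimental design uses the status of cervical precancerous lesions as a stratification variable". Shares are 10/15/20/20/35%, planned HPV rates 10/70/50/70/90%, and the overall rate about 67%. Item C fixes the shares: "After the stratified groups reach the predetermined acceptance ratio, no subjects from this group will be recruited".

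Item F defines the primary statistic from one table without a group index: "According to the definition of the test result, a contingency table can be obtained as follows". Under Test Hypothesis and Verification, H0 is kappa at most 0.66 and H1 is kappa above 0.66, with the success rule "If the test results show that the opposite hypothesis is established, the expected goal of the test is achieved". The sample size section presets kappa at 0.72 and states that "according to the proportion of subjects included in each group, the required samples are 1,049 cases". Table 4 reports the pooled result for all cases.

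Table 5 repeats the same layout for each of the five groups: 2x2 counts, kappa with 95% CI, p value and overall agreement. The secondary indicators include the "consistency evaluation of each group under the test group", and the list of secondary indicators to be analysed repeats it. Outside the primary and secondary indicators, "the rest of the data analysis is exploratory analysis".

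**The concern.** Kappa corrects for chance agreement using the margins of the table. In a pooled table those margins depend on the quotas, which the trial sets. Pooling groups with very different HPV rates lowers the chance term, and the pooled kappa can then exceed most of the group kappas. A reader who sees the groups called a basis for stratification expects a stratified estimate and finds only separate rows.

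At stake would be how a positive result is read. The difference could be as large as the 0.06 between null and planning value. If a combined value were computed only after the data were seen, its weights would be open to choice. In addition, 90% of the women are recruited because of a current or past abnormality, while the protocol's stated purpose is an alternative for women who do not get regular screening.

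**Working it through.** **Inputs.** Shares w = 0.10/0.15/0.20/0.20/0.35 and HPV rates p = 0.10/0.70/0.50/0.70/0.90 (SAP item B); null 0.66; planning value 0.72; power 80%; level 0.05; 1,200 recruited with 10% loss, hence 1,080 valid pairs. Assumptions: the planned HPV rates apply to high-risk HPV; positive and negative agreement with the physician sample are 87% in every group. The documents state neither.

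**1. The plan's own figure.** Overall rate: 0.010 + 0.105 + 0.100 + 0.140 + 0.315 = 0.67, as stated. For a single table with equal margins P = 0.67, the large-sample variance is V(k) = (1−k)[(1−k)(1−2k) + k(2−k)/(2P(1−P))].

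- V(0.66) = 0.34 × (−0.1088 + 2.0000) = 0.6430
- V(0.72) = 0.28 × (−0.1232 + 2.0841) = 0.5491
- n = (1.645√0.6430 + 0.842√0.5491)² / 0.06² = 1,048.2, rounded up to 1,049

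The stated size is reproduced with one pooled rate and a one-sided 0.05 level (two-sided 0.05 gives 1,339). Hypothesis, statistic, Table 4 and N therefore concern the same quantity.

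**2. The size of the difference.** Po = 0.87 throughout.

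- Pooled: the self-sample margin is 0.67 × 0.87 + 0.33 × 0.13 = 0.6258. Pc = 0.67 × 0.6258 + 0.33 × 0.3742 = 0.5428. Kappa = (0.87 − 0.5428)/(1 − 0.5428) = 0.716.
- By group: Pc = 0.7368/0.5592/0.5000/0.5592/0.7368. Kappa = 1 − 0.13/(1−Pc) = 0.51/0.71/0.74/0.71/0.51.
- Stratified, Σn(Po−Pc)/Σn(1−Pc): Σw(1−Pc) = 0.3727, so kappa = 1 − 0.13/0.3727 = 0.651.

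The gap is 0.065. Over the 395 combinations of constant positive and negative agreement with a pooled kappa of 0.70 to 0.74, it is 0.061 to 0.066. So the gap is real under these assumptions.

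**3. Is there one stratified value to report?** The same cells give 0.623 (weights by group size), 0.651 (as above), 0.667 (inverse variance, full variance) or 0.675 (inverse variance, the SAP's SE). The documents favour none of these weightings. The weights n(1−Pc) also use each group's observed margins, so the formula can be fixed in advance but the weights cannot.

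**4. Does the stratified value isolate the recruitment mix?** Hold agreement at 87%/87% and the group HPV rates fixed, and change only the shares:

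| Shares, Groups 1–5 (%) | Pooled | Stratified | Gap |
|---|---|---|---|
| 10/15/20/20/35 (SAP) | 0.716 | 0.651 | 0.065 |
| 60/10/10/10/10 | 0.719 | 0.597 | 0.122 |
| 5/30/30/30/5 | 0.728 | 0.705 | 0.023 |
| 20/20/20/20/20 | 0.735 | 0.659 | 0.076 |

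The pooled kappa moves by 0.02 and the stratified one by 0.11. A quantity that depends more on the mix cannot show how much of the pooled value is due to the mix. What the gap mainly reflects is the spread of HPV rates between groups, combined with kappa's known fall at rates near 10% and 90%. These four mixes are not exhaustive; in extreme ones, such as 92% in Group 5, the pooled value moves too.

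**5. What is already planned.** Every ingredient of a stratified kappa (counts, Po and Pc per group) is in Table 5 or follows from its counts. Group consistency is a listed secondary indicator, so Table 5 falls outside the exploratory remainder. Reporting agreement group by group is a reasonable reading of the protocol's sentence on stratification, which does not promise a combined estimate.

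**The case for a change.** The strongest case for the added line has three parts.

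*It detects something that the pooled test does not.* In simulated trials (1,080 pairs, 87%/87%) the pooled test succeeds about 79% of the time whether the group HPV rates have the planned spread, half of it, or none. Pooled minus stratified averages 0.065, 0.015 and 0.001 in the three cases. This stands as a description of the spread. But the HPV rates in the five groups can be read directly from the margins of Table 5.

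*The gap could be larger.* If the within-group kappa were the same everywhere, 1 − pooled = 0.7417 × (1 − within), because Σwp(1−p)/(P(1−P)) = 0.1640/0.2211. A within-group value of 0.60 then gives a pooled 0.703, and about 59% of trials would succeed. The arithmetic is right. The 0.66 threshold, however, is tested on the pooled kappa, and a pooled 0.703 does exceed it. In that case all five rows of Table 5 would estimate 0.60, and the reader would see it without a summary line.

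*The recruited women are not the intended users.* It is true that a pooled kappa belongs to the mix in which it was measured, and a reader should keep that in mind. A stratified kappa does not help here: it lowers Group 1's weight from 10% to about 7% in the example (0.10 × 0.2632/0.3727). The relevant output is Group 1's own row, which is planned. With about 108 valid pairs its 95% CI is wide, roughly ±0.24 with the SAP's SE (1.96 × √(0.87 × 0.13)/(0.2632 × √108)), so its counts and overall agreement should be read with it. The hypothesis section claims nothing beyond the tested kappa, so there is no claim to narrow.

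**Conclusion.** The concern does not hold. The pooled kappa is a legitimate, pre-specified target, and the threshold, statistic, output table and 1,049 all agree on it. Followed as written, the plan gives a sound result. The gap of about 0.065 (0.061 to 0.066 over the grid) rests on equal agreement in all groups and on the planned rates holding for high-risk HPV; at half the planned spread it falls to about 0.015. It is largely a property of kappa under unequal prevalence and does not signal an error. A combined stratified kappa would change neither N nor the success rule, would have no pass mark of its own, and would depend on a debatable choice of weights (0.623 to 0.675 on the same cells). It would add no information to the group tables already pre-specified. A sponsor may report one if it wishes, but its absence is not a fault. The reproduction of 1,049 assumes a one-sided 0.05 level, which the SAP does not state; nothing in this conclusion depends on it.

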Reactive changes: Inflammation, repair, radiation, and others												
Atrophy with inflammation												
Atypical squamous cells (ASCUS)												
Atypical glandular cells												
Mild dysplasia (CIN1) with koilocytes												
Mild dysplasia (CIN1) without koilocytes												
Moderate dysplasia (CIN2)												
Severe dysplasia (CIN3)												
Carcinoma in situ (CIN3)												
Squamous cell carcinoma												
Adenocarcinoma												
Other malignant neoplasm												
Other												
Atypical glandular cells favor neoplasm												
Atypical squamous cells cannot exclude HSIL												
Dysplasia cannot exclude HSIL												
Endocervical adenocarcinoma in situ												

Table 4 Consistency of high-risk HPV detection in all cases

Physician-collected		Kappa statistic (95% CI)	p value	Overall Agreement
Self-collected	Positive	Negative		
Positive				
Negative				

High-risk HPV types include 16, 18, 31, 33, 35, 39, 45, 51, 52, 56, 58, 59, 66, 68 and other 14 types. The definition of consistency is as follows: high-risk HPV test results are concordant (concordant), the test results of the subject's physician -collected sample and self- collected sample both have any of the above-mentioned high-risk HPV (high-risk HPV positive) or both have no high-risk HPV (high-risk HPV negative); high-risk HPV test results are inconsistent (discordant), the test results of the subject's doctor-collected sample and self-collected sample, one does not have any high-risk HPV, and the other has any of the above- mentioned high -risk types .

Table 5 Consistency of high-risk HPV types detected in each group

Self-collected	Physician-collected		Kappa statistic (95% CI)	p value	Overall Agreement
	Positive	Negative			
Group 1					
Positive					
Negative					
Group 2					
Positive					
Negative					
Group 3					
Positive					
Negative					
Group 4					
Positive					
Negative					
Group 5					
Positive					
Negative					

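### The SAP's printed standard error of kappa treats chance agreement as known and does not reproduce the stated 1,049; the effect is small in the primary table and depends on an unstated kappa in Groups 1 and 5

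*SAP*

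**What the plan says.** Item F (SAP, Statistical design, methods and analysis procedures) defines kappa as (P0 − Pc)/(1 − Pc), with Pc computed from the observed row and column totals. It continues: "The standard error of the Kappa statistic is based on" a cited 1969 paper, and sets SE(K) = SD(K)/√N with SD(K)² = P0(1 − P0)/(1 − Pc)². The "interval estimate of the Kappa statistic is" K ± z × SE(K).

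The hypotheses are kappa ≤ 0.66 against kappa > 0.66. Under Sample size calculation, "The above-mentioned kappa value is preset to be 0.72", and "under the condition that the test power is 80% and the significance level is 0.05" "the required samples are 1,049 cases". That section names neither a variance formula nor a side for the test. In the design section the "overall HPV positive rate is expected to be about 67" per cent, built from group rates of 10%, 70%, 50%, 70% and 90%.

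The table shells plan a kappa with 95% CI and p value overall (Table 4), by group ("Table 5 Consistency of high-risk HPV types detected in each group"), for any HPV type (Table 6) and for type groupings (Table 7).

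**The concern.** Because Pc is estimated from the same table as P0, the sampling variance of kappa has to allow for both. The printed expression is the variance of P0 divided by the constant (1 − Pc)². With equal margins it equals the full variance only at 50% positivity, and the plan expects 67% overall and 10% and 90% in Groups 1 and 5.

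Two things are at stake. The sample size and the analysis appear to rest on different variances, so a reader who applies the SAP's only printed formula cannot recover 1,049. Also, if item F's interval is carried into the group tables, the error could be larger there, because positivity is far from 50%.

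**Working it through.** **Inputs.** From the SAP: null kappa 0.66, design kappa 0.72, power 80%, level 0.05, overall positivity 0.67, group positivity 10% (Group 1) and 90% (Group 5), planned group sizes 120 and 420, up to 10% loss. Assumed: equal margins, and a one-sided level, because the alternative is directional.

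**Variances (per subject).** Let p_ij be the cell proportions and r_i, c_i the row and column margins.
- Printed: P0(1 − P0)/(1 − Pc)².
- Full (delta method): {Σ p_ii[1 − (r_i + c_i)(1 − K)]² + (1 − K)² Σ_{i≠j} p_ij(c_i + r_j)² − [K − Pc(1 − K)]²}/(1 − Pc)².

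**Step 1: the plan's 1,049.** Pc = 0.67² + 0.33² = 0.5578. P0 = Pc + K(1 − Pc), which is 0.8497 at kappa 0.66 and 0.8762 at 0.72.

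N = [(1.645√V(0.66) + 0.8416√V(0.72))/0.06]²

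| Variance | V(0.66) | V(0.72) | N | Power at 1,049 |
|---|---|---|---|---|
| Full | 0.6430 | 0.5491 | 1,048.2 → 1,049 | 80.0% |
| Printed | 0.6533 | 0.5548 | 1,063.1 → 1,064 | 79.5% |

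The full variance returns the stated figure exactly. The printed one needs 15 more. Two-sided versions give 1,339 (full) and 1,358 (printed), so 1,049 also requires a one-sided 5% level.

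**Step 2: primary table.** SE ratio, printed to full: √(0.5548/0.5491) = 1.005 at kappa 0.72 and √(0.6533/0.6430) = 1.008 at 0.66.

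**Step 3: Groups 1 and 5, equal margins.** At 10% or 90% positivity, Pc = 0.82.
- Kappa 0.72: P0 = 0.9496, printed 0.9496 × 0.0504/0.18² = 1.4772, full 1.3991. Excess in SE 2.7%. The 95% half-width is 0.217 against 0.212 in Group 1 (n = 120) and 0.116 against 0.113 in Group 5 (n = 420).
- Kappa 0.62: printed 1.9667, full 1.7716. Excess 5.4%. Half-width 0.25 against 0.24 in Group 1 and 0.134 against 0.127 in Group 5.

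The value 0.62 arises as follows. A pooled kappa of 0.72 means pooled disagreement of 1 − 0.8762 = 0.1238. The recruitment-weighted average of 2p(1 − p) over the five groups is 0.018 + 0.063 + 0.100 + 0.084 + 0.063 = 0.328. A kappa common to all groups would then be 1 − 0.1238/0.328 = 0.62. Pooling groups with very different positivity raises the overall kappa above the within-group values.

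**Step 4: Groups 1 and 5, unequal margins.** Suppose self-sampling reproduces a fixed share of physician positives and of physician negatives in every group. These pairs are assumptions, chosen to give a pooled kappa near 0.72.

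| Positives / negatives reproduced | Pooled kappa | Table 4 SE excess | Group 1 kappa, SE excess | Group 5 kappa, SE excess |
|---|---|---|---|---|
| 90% / 83% | 0.72 | 0.5% | 0.45, 17% | 0.55, 9% |
| 87% / 87% | 0.72 | 0.8% | 0.51, 12% | 0.51, 12% |
| 85% / 90% | 0.71 | 1.3% | 0.56, 9% | 0.48, 14% |
| 80% / 98% | 0.71 | 3.7% | 0.79, 1.6% | 0.44, 20% |

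**Step 5: simulated coverage of the 95% interval.** With 10% loss (120 × 0.9 = 108; 420 × 0.9 = 378), the printed interval covers about 97% in Group 1 at 90%/83% and about 98% in Group 5 at 80%/98%. The full-variance interval in Group 1 covers about 93% at 90%/83% and about 90% at 80%/98%.

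**The case against.** A reader might infer that the Group 1 and Group 5 intervals are materially too wide as planned. The documents do not support that. They give no group-level kappa and none of the pairs in Step 4. If within-group kappa equals the design value and margins are equal, the excess is under 3%, and the printed interval is not over-wide in simulation: in Group 1 (n = 120, kappa 0.66 to 0.72) it covers about 93.5%, against 92.0% to 92.3% for the full variance, and in Group 5 (n = 420) 94.8% to 95.3% against 94.0% to 94.4%. At 80%/98% the Group 1 excess is only 1.6%, and both intervals under-cover, at about 90%. For rare types (2% to 5% prevalence, kappa 0.72, n = 1,049) the excess is 3.4% to 3.9%, and the printed interval is again nearer to nominal. All of this stands, and it makes the group-level effect conditional.

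It is also an inference that Tables 5 to 7 would use item F's formula. The formula stands beside the high-risk HPV table, the type-specific sentence names only kappa or related tests, and the shells give no variance. The SAP says the analysis is done in SAS without naming a procedure. This stands too.

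A reader might further infer that the SAP misquotes its source. That cannot be judged without the paper, and the point does not need it.

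Finally, the primary conclusion is hardly touched. With 10% loss from 1,200, 1,080 pairs remain, more than 1,064; at 1,200 pairs power is 84.3% on the printed variance and 84.7% on the full one. This is right, and it limits the importance of the point. It does not explain why the only printed variance fails to return the plan's own sample size.

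**Conclusion.** The point holds as a wrong formula of small consequence. The printed SE omits the sampling error of Pc, and it is not the variance behind 1,049 (1,064 against 1,049, or about half a percentage point of power), assuming equal margins and a one-sided 5% level. In Table 4 it is about 0.5% to 4% too large, which errs on the cautious side. In Groups 1 and 5, if item F's interval is used there, the excess is about 3% to 5% for within-group kappa of 0.62 to 0.72 with equal margins, and about 9% to 20% for kappa nearer 0.44 to 0.56. Which applies cannot be settled from the plan. Since 0.72 is set for the overall comparison, assuming the same value within Groups 1 and 5 is a favourable case.

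**What to change.** In item F, replace the printed SE with the full large-sample (delta-method) variance of kappa, and state that it applies to the primary test and to the kappa intervals in Tables 4 to 7. Under Sample size calculation, add that 1,049 uses this variance with a one-sided 5% level.

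The cost is one formula and one sentence, with no change to recruitment. There is a small downside: the full-variance interval is slightly narrower than the printed one and under-covers in Group 1 (about 90% to 93% at n near 108). So specify a bootstrap or other small-sample interval for Group 1 and for rare types.
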